All supplies for the study will be accompanied by accountability and shipping documents and will be maintained by the Investigator or deputy (e.g. research pharmacist). Information recorded on these accountability and shipping documents will include relevant dates, batch numbers, quantities received or dispensed, to whom dispensed, returned drug and drug lost or damaged. At the end of the study, all used and unused Omegaven® will be accounted for. If expired, the remaining drug supplies will be destroyed.

Details of Omegaven® Administration

After baseline labs are obtained (Tables 2 and 3), therapy with Omegaven® will be initiated at the goal dose of 1 gram /kg/day and is infused over 8-24 hours, so long as the infusion rate does not exceed 0.15g/kg/hour. Omegaven® will be infused intravenously through either a central or peripheral catheter alone or in conjunction with parenteral nutrition. If additional fat calories are needed, they will be provided via the enteral route. The same standards of care provided to all patients receiving parenteral nutrition solution will be followed. Routine nutritional monitoring is described in Table 3.

In the event that a patient is unable to achieve adequate calories parenterally and is unable to tolerate enteral feeds, it may be necessary to evaluate whether or not the patient should continue the study with Omegaven® as monotherapy or resume therapy with conventional fat emulsions so that additional parenteral fat calories can be given. The clinical team, in conjunction with the patient's primary physician, will determine if the patient should be removed from the protocol. The DSMB will also be notified.

Orders for Omegaven® will be written on a CHB PN order form and must contain the following data elements:

- Total daily dose to administered in mL
- The hourly infusion rate (total daily dose ÷ the number of hours to be infused)

Prior to the administration of each Omegaven® dose, two nurses will check the dose dispensed against the physician's orders and verify that the infusion pump settings (hourly rate, volume to be infused) are correct before the infusion is started.

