Limited access, need to administer incompatible medications	Stop Omegaven® infusion, flush catheter with either NS or dextrose, administer incompatible medication, flush catheter, resume infusion; may be necessary to infuse Omegaven® over 8 -24 hours. Multiple syringes should be used so as to keep maximum hang time of Omegaven® source container less than 12 hours) Regardless of the infusion time, the infusion rate cannot exceed 0.15g/kg/hour.

Discontinuation of Therapy

Patients will continue to be followed by the Center for Advanced Intestinal Rehabilitation (CAIR) Program upon discontinuation of therapy with Omegaven® for a minimum of 2 months after the treatment is stopped.

Resumption of Therapy

For patients who have been off the protocol more than 1 year, in the event that the patient must receive intravenous fat emulsion, treatment with Omegaven® will resume only if the patient shows evidence of PN liver damage (elevations in direct bilirubin ≥ 2 or pathology findings consistent with cholestasis). Otherwise, the patient will be treated with conventional fat emulsion.

Soybean based Fat Emulsion (Intralipid® and/or Liposyn®)

Subjects in the Andorsky et al cohort received one of two commercially available intravenous fat emulsions (IFE), Liposyn® II or Intralipid®. IFE is provided as an oil-in-water emulsion derived from egg phospholipids, soybean or safflower oils and glycerol. Although three concentrations are commercially available (10, 20, 30%) only the 10 and 20% concentrations have been approved for use in children. Both Liposyn® II and Intralipid® contain soybean oils. Table 1 summarizes the composition of both products.

Details of IFE Administration

Regardless of the product used, doses less than 96 ml/day were repacked into syringes to allow for administration via syringe pump. Doses greater than 96ml/day were dispensed in the original manufacturer's container. If patients were discharged home on either IFE, all doses were administered from the original manufacturer's container.

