A Committee of the Study Investigators (Drs. [name], [name], and [name]) will be responsible for assuring that adverse event reporting requirements are actually met. The Investigator Committee will meet not less than monthly to conduct clinical case reviews of all patients receiving Omegaven® to review recruitment data, adverse events and protocol deviations; and to evaluate overall safety of Omegaven® therapy. CHB Staff dieticians caring for Omegaven® patients will participate in the Investigator meetings as necessary. Any patients who have agreed to participate in the trial, but who have not yet undergone intervention, will be informed of adverse events. A revised consent document will be submitted to the CCI with the adverse event form for review and approval. All adverse events will be classified by the Principal Investigator as definitely, probably, possibly, or unrelated to administration of study drug.

Patients will be withdrawn from the study for any of the following:

- a) Toxicity considered unacceptable by the Principal Investigator
- b) Patient/guardian requests to discontinue treatment and/or observation for any reason.
- c) A suitable organ has been located and the patient is able to undergo a liver or liver/intestinal transplant.
- d) Decision by the Principal Investigator that termination is in the patient's best medical interest.
- e) Patient is lost to follow up.

In the event that a patient is withdrawn from the protocol, study staff will document the date of withdrawal, the reason for withdrawal, and the results of all measurements of interest made up to date of withdrawal.

5. Data Management and Statistical Analysis

a. Data Management Methods

Overview

All clinical and laboratory research data will be abstracted from source documents (medical records) and recorded and maintained on study specific case report forms (CRF). These CRFs will be stored within individual subject binders in accordance with Good Clinical Practice Standards and FDA requirements. Study materials will be kept in the Principal Investigator's locked office and access will be restricted to authorized study staff only. Subject confidentiality will be maintained by recording subject-specific data using a unique confidential study identifier.

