Individual patient medical information obtained as a result of this study is considered confidential and disclosure to third parties, other than those cited below, is prohibited. Patient confidentiality will be further ensured by utilizing patient identification code numbers and patient initials. Data generated as a result of this study will be available for inspection, on request by various regulatory agencies. These shall include

all study-relevant documentation, including medical histories to verify eligibility, laboratory test results to verify transcription accuracy, treatment and diagnostic reports, admission/discharge summaries for hospital admissions occurring while the patient is on study, and autopsy reports (if available) for deaths occurring during or in temporal proximity to the study.

As part of the required content of the informed consent, patients must be informed that their records will be reviewed by various regulatory agencies.

Retention of Records

The study coordinator will maintain a comprehensive and centralized filing system of all study related documentation which is suitable for inspection at any time by various regulatory agencies. These include:

- a. Patient files including source documentation and Informed Consent
- b. Study files, including the protocol with all amendments, copies of all regulatory documentation, and all correspondence with the FDA and IRB
- c. Pharmacy files including drug shipment, dispensing, and accountability records, and pharmacy-related correspondence

Per FDA regulations, the Primary Investigator will retain records for a period of five (5) years following discontinuation of the study.

Data Quality and Completeness

Allowable ranges were created for each variable of interest and records outside of those ranges were checked.

c. Data Analysis Plan

Using graphical methods (including boxplots) and descriptive statistics, we will assess assumptions required for validity of statistical methods and presence of outliers. Continuous variables will be summarized via means (and standard deviations) or medians (and interquartile ranges, when appropriate). When appropriate variables will be transformed.

Primary analyses of the primary outcome will be based on the intention-to-treat analysis i.e., patient will be considered receiving either omegaven® or soybean based emulsions throughout the whole follow-up period, regardless of temporary discontinuation of treatment due to infections or other causes.

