We will also compare nutritional outcomes of the two groups including difference in weight-for- age Z-scores and height-for-age Z-scores from baseline to the moment in which the child starts enteral feeding and to the moment in which the child receives less than 10% of their calories from PN. Comparison between study groups will be performed via t-test or Wilcoxon tests, as appropriate. Using linear regression, we will explore adjustment for baseline alternative predictors of interest. Trends over time in Z-scores will also be explored using regression with repeated measure methods.

Analysis of Efficacy of Omegaven®

The primary outcome to gain preliminary evidence of efficacy will be based on the time from baseline to normalization of bilirubin level, i.e, first time point among three consecutive in which bilirubin is < 2 mg/dL. We do not anticipate that any subject will present a rebound on direct bilirubin after normalization. However, we will describe the cohort with respect to the frequency of rebounds in bilirubin levels.

Crude comparisons of time to normalize direct bilirubin levels between Omegaven® and soybean oil fat emulsion patients will be based on Kaplan-Meier curves and log-rank tests. We will estimate hazard ratios and adjust for potential baseline confounders using Cox-proportional hazard models. For all survival analysis based on non-parametric or semi-parametric methods, we will attribute an infinite time to event (i.e., time to event larger than the largest follow-up time in the whole study population) for subjects who die or receive a liver transplant before bilirubin is normalized. Subjects who die before their bilirubin levels normalize (particularly due to liver failure) have in fact the worse outcome (infinite time to normalize bilirubin) and were not censored before reaching the endpoint of interest. Results of these analysis will be compared with results of analysis excluding subjects who die or are transplanted. Time to reach a total bilirubin of 1.2 will also be compared using survival analysis methods. Analysis of this outcome will proceed as described for direct bilirubin.

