Differences in the frequency of the event between Omegaven® and historical control groups	Frequency of the event in one of the comparison groups	Fisher's Exact Test		
		20	25	30
35%	5%	72%	82%	89%
	25%	49%	65%	72%
	50%	57%	68%	78%
45%	5%	89%	95%	98%
	25%	73%	88%	92%
	50%	89%	95%	98%

*Calculations performed using N-query advisor.

e. Study Organization

[name] will serve as the principal investigator. [name] will serve as the managing co-investigator. [name], [name], [name], [name], and [name] will assist with patient enrollment. Drs. [name], [name], and [name] along with the CRP staff will assist in study design and data analysis. Data collection will be done by the research nurses, with assistance from the nursing unit liaisons, the study coordinator, and research assistants in [name] lab. All individuals who assist in this function will have CITI training. The necessary CCI amendments and approvals will be obtained prior to any staff assisting in this function. The study coordinator will abstract the medical records and complete the CRFs and a careful QC visual inspection of the CRFs prior to submitting them for data entry. The Research Coordinator will complete all data entry..

f. Data and Safety Monitoring Plan

Patients will be monitored while receiving Omegaven® treatment to observe for signs of Omegaven® toxicity. At the start of Omegaven® therapy, patients will be monitored closely during and shortly after initial Omegaven® administration to observe for signs of allergic reaction and anaphylaxis. In the event the patient demonstrated signs or symptoms of allergic reaction, the Omegaven® will be discontinued and the PI and attending physician will be notified. Selected safety labs will be evaluated by attending staff

and the Study Investigators for both clinical and research purposes. Blood samples will be taken prior to the start of therapy (baseline), and thereafter in accordance with the scheduled represented in the tables below.

Reversal/Safety Study Lab Schedule:

Patient Status	Parameter	Tests to be Performed	Frequency
Inpatient/receiving Omegaven®	Direct bilirubin >2 mg/dL	PN profile, AST, GGT, CRP, lipid Panel, PT, PTT, INR, fibrinogen, EFA Panel	Weekly
	Direct bilirubin ≤2 mg/dL	PN profile	Weekly
		PN profile, AST, GGT, CRP, PT, PTT, INR, fibrinogen, EFA panel, lipid panel	Monthly
Inpatient/off Omegaven®			
		PN profile, AST, GGT, CRP, lipid Panel, PT, PTT, INR, fibrinogen, EFA Panel	one complete set of post-Omegaven labs

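### No rule covers Omegaven patients withdrawn alive before bilirubin normalizes, and recording is specified only to the withdrawal date; if withdrawal tracks prognosis, this could favour Omegaven

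*Combined protocol and SAP*

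**What the plan says.** - **Withdrawal (section 4h, Adverse Event Criteria and Reporting Procedures).** Reasons for leaving the study include a) unacceptable toxicity, c) "A suitable organ has been located and the patient is able to undergo a liver or liver/intestinal transplant" and d) "Decision by the Principal Investigator that termination is in the patient's best medical interest". Staff record the date, the reason and "the results of all measurements of interest made up to date of withdrawal". No later collection is described.
- **Removal (section 4d, Details of Omegaven Administration).** If a patient cannot get enough calories and does not tolerate feeds, return to conventional emulsion is considered. The clinical team, with the primary physician, "will determine if the patient should be removed from the protocol". Nothing is said about data after that.
- **Death and transplant window (section 4e).** The window is the period of Omegaven treatment for treated patients, and all available data for the main historical cohort.
- **Intention-to-treat (section 5c, Data Analysis Plan).** Patients stay in their group for the whole follow-up "regardless of temporary discontinuation of treatment due to infections or other causes".
- **Primary efficacy analysis (section 5c, Analysis of Efficacy).** Kaplan-Meier, log-rank and Cox methods are used, with an infinite time to event "for subjects who die or receive a liver transplant before bilirubin is normalized".
- **After stopping.** Discontinuation of Therapy (section 4d) promises program follow-up "for a minimum of 2 months after the treatment is stopped". The lab schedule in section 5f gives inpatients off Omegaven "one complete set of post-Omegaven labs" and has no off-Omegaven row for outpatients.

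**The concern.** The primary comparison sets a prospectively followed group, which has a written exit rule, against controls taken from existing records, which have none. Under the plan, controls stayed on soybean emulsion until weaned. Reasons a) and d), and removal for inadequate nutrition, could plausibly select patients who are doing badly. If such patients leave the Omegaven risk set while similar controls stay in it, the Omegaven curve rises without any drug effect.

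The unequal death/transplant windows raise a second problem, for hypothesis 2.4. A death or transplant after withdrawal could be counted in controls and missed in the Omegaven group. The infinite-time rule cannot be applied to an event that nobody recorded. Growth data (hypothesis 1.3) on patients who could not be nourished on Omegaven would stop in the same way.

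**Working it through.** **Step 1. Place each exit before normalization under the written rules.**

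| Exit | Recording stated | Place in primary analysis |
|---|---|---|
| Temporary interruption | Continues | Counted throughout (intention-to-treat sentence) |
| Observed death; transplant (reason c) | Yes | Infinite time |
| Toxicity (a), investigator decision (d) | To withdrawal date | None stated; censored by default |
| Removal for inadequate calories (4d) | Not stated there; most naturally read under the 4h sentence | None stated; censored by default |
| Family request (b), loss to follow-up (e) | To withdrawal date | None stated; censoring is usual |
| Death or transplant after withdrawal | 4e window ends with treatment | Infinite-time rule unusable if unrecorded |

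No other rule fills the gap. Missing Values interpolates at most two missing visits in mid-follow-up. The comparison analysis under Analysis of Efficacy drops deaths and transplants but does not mention withdrawals.

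**Step 2. Ask whether post-treatment labs rescue the endpoint.** Section 4e requires three values in a row at or below 2 mg/dL, or one such value plus weaning. A patient returned to soybean emulsion is still on PN and needs three. One required inpatient set cannot show that.

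**Step 3. Size.** The plan gives no withdrawal rate, event count or power for this endpoint, so there is no figure to reproduce. All inputs below are assumptions, and the true hazard ratio is 1.

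*Model A.* In both groups 60% normalize, with exponential times and a median of 12 weeks; follow-up ends at 104 weeks; controls are fully followed. A share w of the Omegaven group, all never-normalizers, is censored uniformly over weeks 2-12.

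Hand check of the one-year curve:
- Without withdrawal: 0.60 × (1 − 2^(−52/12)) = 0.60 × (1 − 0.050) = 0.57.
- If the withdrawn left at time zero, the curve would be 0.57/(1 − w): 0.60, 0.63 and 0.71 for w = 5%, 10% and 20%.
- Simulated, with exits spread over weeks 2-12: 60%, 62-63% and 69%. These agree in direction and are slightly lower at 20%, as expected with later exits.

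*Model B.* 30 per group, 24 months of follow-up, median 6 months among normalizers, 20% or 40% never normalizing, withdrawal uniform over months 0-6, 3,000 runs.

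| Estimated hazard ratio for normalization (above 1 favours Omegaven) | w = 5% | 10% | 20% |
|---|---|---|---|
| A, all withdrawn are failures | 1.06 | 1.13-1.15 | 1.33 |
| A, half taken from failures, half at random | 1.02 | 1.06 | 1.13 |
| B, 40% never normalize, all withdrawn are failures | 1.05 | 1.14 | 1.33 |
| B, 20% never normalize, all withdrawn are failures | 1.08 | 1.19 | 1.52 |

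In Model B, two-sided rejection at a nominal 5% is 5%, 7% and 14% (40% never normalizing) or 6%, 9% and 27% (20%).

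The hazard ratio returns to about 1 in three cases:
- withdrawal unrelated to prognosis: 1.00-1.01 (A), 0.99-1.02 (B);
- the same patients kept to the end as not normalized: 0.99-1.01 (B);
- controls losing never-normalizers at the same rate: 1.00-1.01 (A).

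**Step 4. How extreme is the top of the range?** The share of Omegaven failures that must leave is w divided by the share never normalizing. For 1.52 it is 0.20/0.20 = 100%; for 1.33 it is 0.20/0.40 = 50%. Neither model includes death or transplant.

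**The case against.** A reader might infer that data collection ends on return to soybean emulsion, that failing patients are censored in the Omegaven group only, that this contradicts intention-to-treat, and that the primary result is inflated. The documents do not support these readings:

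- Section 4d is silent on data after removal. Section 4h says what will be documented, not that later collection is barred. Results come from hospital charts and standard-care tests, and at least two months of follow-up are promised after treatment stops.
- Censoring at withdrawal is an inference; the plan never states it. The clearest hepatic failures, observed deaths and transplants, get infinite time.
- The intention-to-treat sentence names only temporary interruptions. Permanent discontinuation is uncovered, which is a gap and not a contradiction.
- Removal for inadequate calories is not triggered by bilirubin, and toxicity may not be hepatic. A link to prognosis is plausible, not shown.
- Potential Study Limitations expects more missing data in controls, so complete control follow-up is an assumption.
- The lab schedule is a minimum. The outpatient monthly row runs until the patient is off Omegaven and has at least one bilirubin below 2 mg/dL, so it may extend past stopping.

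All of this stands, and it makes the concern conditional. It does not close the gap. The two-month promise does not say that results enter the analysis, and it sits uneasily with the 4h sentence. The 4e windows differ as written. Missing control data cannot be assumed to offset the problem, because the limitations section says it could itself overstate the Omegaven effect.

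**Conclusion.** The concern holds in conditional form. The plan specifies recording only to withdrawal, limits Omegaven death/transplant collection to treatment, and gives no rule for a patient withdrawn alive before normalization. Standard survival methods would then censor that patient.

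The direction of bias favours Omegaven only if withdrawal is linked to poor prognosis and controls do not lose similar patients to the same extent. Under those assumptions the illustrative hazard ratio is about 1.05 to 1.5 for 5% to 20% withdrawn: small at 5%, material at 20%. It is near 1.0 if withdrawal is unrelated to prognosis. The actual size cannot be found from the documents. The study seeks only preliminary efficacy evidence and already declares its groups non-comparable, but its limitations section does not name this route and no planned sensitivity analysis would reveal it.

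**What to change.** 1. In sections 4d and 4h, separate stopping Omegaven from ending observation. Where consent allows, keep abstracting direct bilirubin, PN status, weight and height, transplant and death through the same endpoint window as for other patients.
2. In section 4e, align the death/transplant window so that it does not end with Omegaven treatment.
3. In section 5c, extend the intention-to-treat sentence to permanent discontinuation and return to soybean emulsion.
4. State that censoring before the end of follow-up is limited to withdrawn consent for observation and loss to follow-up. Add a sensitivity analysis that keeps every patient withdrawn before normalization as not normalized. This is an unfavourable bound, since some of them might have normalized.
5. Reconcile the two-month follow-up in Discontinuation of Therapy with section 4h and the section 5f lab schedule, or state that rebound is described mainly on treatment.

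The cost is wording in a few sections and slightly more chart abstraction of standard-care values. The estimate will include time off drug and may be less favourable to Omegaven. No treatment decision changes.

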As previously mentioned, Omegaven® may be infused in the same manner as conventional fat emulsions through either a central or peripheral line. The emulsion is isotonic. It is compatible with parenteral nutrition solutions and may be co-infused via y-site. Per Infection Control, source containers must be changed every 12 hours and unused product discarded. Omegaven® may be infused through a 1.2micron inline filter.

Dose Modification

Lipid Intolerance

If lipid intolerance develops, defined as serum triglyceride levels > 200 mg/dL, the following will be considered prior to reducing the dose:

- a) If the level was obtained while the patient was receiving a continuous 24-hour infusion of Omegaven®, the total dose should be infused over 20 hours, and a repeat serum triglyceride level obtained prior to resuming the infusion 4 hours later.

b) Other sources of lipid intolerance should be considered and addressed (drugs, renal disease)

If the triglycerides continue to remain high despite the aforementioned interventions, a dosage reduction of 25% of the current dose will be considered.

High Glucose Infusion Rate

Subjects with a high glucose infusion rate (GIR) will have a dose increase up to 1.5 grams/kg/day to allow for a reduction in PN calories from carbohydrates at the discretion of the Omegaven study team and the nutrition service.

Duration of Therapy

Patients will remain on Omegaven® until weaned from PN. Patients may continue monotherapy with Omegaven® as an additional source of calories after the dextrose/protein portion of PN is discontinued

In the event that a patient who has been listed for a liver or liver/intestinal transplant has an organ become available, the participation in this protocol will not preclude them from receiving the transplant.

Disruption of Therapy

In event that Omegaven® cannot be administered (i.e. loss of central venous catheter access, fluid restrictions, need to administer an incompatible medication/blood product), the infusion of Omegaven® may be interrupted and resumed when the conflicting situation is resolved. Some potential interventions that can be used include:

Situation	Possible Solution
Loss of central venous access	Administer via peripheral route
Fluid restriction	Consult with pharmacy to concentrate PN, medications to allow for administration

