Adverse events (AEs) will be assessed and reported from the time of the first Omegaven® infusion until exit from the study in accordance with CHB Committee on Clinical Investigations (CCI) reporting requirements. In particular, the patient will be observed during and shortly after Omegaven® administration for the occurrence of anaphylactic or allergic reactions. Other expected adverse events include death, blood stream infection; transfer to ICU for treatment of respiratory distress or hemodynamic instability; re-hospitalization for treatment of blood stream infection, dehydration, electrolyte abnormalities, catheter malfunctions, bowel obstructions, and urinary tract infection. Unexpected adverse events will also be assessed and reported in compliance with the CHB CCI requirements. Patients experiencing any adverse events that are moderate or severe in nature and that may be related to Omegaven® will have their treatment temporarily halted until the adverse event has resolved. Dose modifications will occur as described above. If a dose reduction is made for adverse events later considered to be unrelated to Omegaven®, the Omegaven® dose will be increased back to the dose prescribed prior to the dose reduction. Patients with anaphylactic or allergic reactions will not continue Omegaven® treatment.

Any serious or unsuspected adverse events will be reported to the Committee on Clinical Investigation (CCI) and the FDA within 72 hours of the occurrence of being known, or immediately if the event is fatal or life threatening as per Children's Hospital Policy on Adverse and Unexpected Events and Unanticipated Risks to Research Subjects and Others. This will be done in person, by telephone, or email, and by completion of the CCI's form for adverse/unexpected event reporting.

Adverse events are detected by CHB acute care medical and nursing staff during provision of standard care services including the routine monitoring of vital signs and daily physical exam data. Adverse events identified by CHB staff are reported to the Principal Investigator immediately by telephone or pager, and subsequently to the appropriate board or committee.

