A limited tolerance for deviations in Omegaven® dosing will be allowed to accommodate expected variations that commonly occur when providing standard clinical care of pediatric patients receiving nutritional supplements including essential fatty acids. For example, in cases where patients are also prescribed medications that are incompatible with Omegaven®, (e.g. morphine) dosing may vary up to a 1.5 hour dose equivalent. Omegaven® infusion may also be stopped / postponed when a patient goes for special diagnostic studies or procedures or therapeutic treatments. An Omegaven® dose range will be established for protocol deviation reporting such that Omegaven® dosing will be set at target (1 gram of Omegaven® per kilogram of body weight per day) plus or minus a 1.5 hour dose equivalent. Dosing variations that exceed the tolerance range will be reported to the CCI as protocol deviations.

6. Specimen Collection/Laboratory Testing / Laboratory results data capture:

All laboratory studies captured for the Omegaven® compassionate use protocol are considered standard care laboratory tests for this patient population. No additional QA procedures will be established beyond the QA procedures already established as CHB standard operating procedures for patient care, specimen collection, processing, storage, shipping and results reporting. If specimens are not drawn on schedule, if specimen volume is insufficient, or if specimen are contaminated or destroyed such that laboratory test results are missing or deemed invalid for any reason, laboratory values will be recorded as missing on the laboratory CRFs and in the CDMS. If any of the following laboratory values are missing at baseline or for 2 consecutive cycles, a report of a protocol deviation will be reported to the CCI and DSMB:

- Serum triglycerides;
- Coagulation labs, PT, PTT, INR;
- Essential Fatty Acid Profile;
- Direct and total bilirubin values;

Re-training of clinical, research and/or laboratory staff will be conducted if safety labs or primary outcome lab values are missing on two consecutive occasions.

7. Data Capture:

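### Minor, wrong as written: the dosing-deviation range is fixed around 1 g/kg/day although other doses are permitted, so a modified-dose patient wrongly given 1.0 is not flagged by this rule

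*Combined protocol and SAP*

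**What the plan says.** Under Quality Control Method, in the item on Omegaven administration, the protocol allows a limited dosing tolerance "to accommodate expected variations that commonly occur when providing standard clinical care". Its examples are incompatible medications and interruptions for procedures. The range for deviation reporting is "set at target (1 gram of Omegaven® per kilogram of body weight per day) plus or minus a 1.5 hour dose equivalent". The consequence follows: "Dosing variations that exceed the tolerance range will be reported to the CCI as protocol deviations".

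Other sections make other doses compliant:

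- Dose Modification, Lipid Intolerance: if triglycerides stay high after the first measures, "a dosage reduction of 25% of the current dose will be considered".
- Dose Modification, High Glucose Infusion Rate: these subjects "will have a dose increase up to 1.5 grams/kg/day", at the discretion of the study team and the nutrition service.
- Adverse Event Criteria and Reporting Procedures: after a reduction for an event later judged unrelated, "the Omegaven® dose will be increased back to the dose prescribed prior to the dose reduction". This section therefore works from the prescribed dose, not a fixed one.
- Data and Safety Monitoring Plan: bleeding is a further reason for reduction, with no size given.

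Details of Omegaven Administration sets an infusion time of 8 to 24 hours, "so long as the infusion rate does not exceed 0.15g/kg/hour". It also requires that "two nurses will check the dose dispensed against the physician's orders".

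**The concern.** A dosing-deviation rule should compare what a patient received with what that patient was meant to receive. This one compares it with a constant. Once the dose has been changed under the protocol, the rule has the wrong reference point.

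The main consequence is a missed report. A patient reduced to 0.75 g/kg/day who is mistakenly given the old dose of 1.0 receives exactly the value that the rule treats as perfect. So does a patient raised to 1.5 who is given 1.0. The first case matters more: the dose was lowered because triglycerides stayed above 200 mg/dL, and the risk section links levels above 200 to fat overload syndrome.

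The second consequence is conditional. If ordered changes count as dosing variations, a correctly given 0.75 or 1.5 is itself reportable to the CCI.

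What is at stake is the accuracy of dosing-deviation reports for patients on a modified dose.

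**Working it through.** The plan gives no numerical limits for the range, so there is no printed figure to reproduce. The limits follow from its own inputs.

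**Inputs.** Fixed target 1 g/kg/day and tolerance of 1.5 hours of dose (Quality Control Method). Infusion time h of 8 to 24 hours and maximum rate 0.15 g/kg/hour (Details of Omegaven Administration). Permitted doses of 0.75 (25% off 1.0) and up to 1.5 g/kg/day (Dose Modification).

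**Step 1: the range as written.** Limits are 1 ± 1.5 × (1/h).

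- 24 h: 1.5/24 = 0.0625, giving 0.9375 to 1.0625.
- 8 h: 1.5/8 = 0.1875, giving 0.8125 to 1.1875.
- Outer bound, taking the 1.5 hours at the maximum rate: 1.5 × 0.15 = 0.225, giving 0.775 to 1.225.

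Both 0.75 and 1.5 lie outside even the outer bound, and 1.0 is always at the centre.

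**Step 2: size of the error that is not flagged.**

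- Ordered 0.75, given 1.0: 1.0/0.75 = 1.33, an excess of 33%.
- Ordered 1.5, given 1.0: 1.0/1.5 = 0.67, a shortfall of 33%.

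**Step 3: is every correct modified dose outside the range?** No. An ordered 1.1 g/kg/day differs from 1.0 by 0.1, and 0.1 ≤ 1.5/h whenever h ≤ 15. It therefore stays inside the fixed range for infusions of 15 hours or less.

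**Step 4: the range centred on the ordered dose d.** Limits are d ± 1.5 × (d/h). An order of 1.5 needs at least 1.5/0.15 = 10 hours.

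| Ordered dose (g/kg/day) | Shortest infusion shown | 24 h infusion | Contains 1.0? |
|---|---|---|---|
| 0.75 | 8 h: 0.609 to 0.891 | 0.703 to 0.797 | No |
| 1.5 | 10 h: 1.275 to 1.725 | 1.406 to 1.594 | No |

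A mistaken 1.0 is now flagged in all four cases, and the correct modified dose is not reportable.

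**Step 5: what re-centring still misses.** A mistaken 1.0 is flagged only when d < 1/(1 + 1.5/h) or d > 1/(1 − 1.5/h).

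- 10 h: below 0.870 or above 1.176.
- 24 h: below 0.941 or above 1.067.

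An order of 1.125 (25% off 1.5) shows the limit. Over 10 hours its range is 0.956 to 1.294, which contains 1.0, so the error is missed. Over 24 hours it is 1.055 to 1.195, so the error is flagged.

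**The case against.** The strongest reply is that the target means each patient's goal dose, with 1 g/kg/day given only as the default. The tolerance is written for interruptions to an intended infusion, and the administration section describes 1 g/kg/day as the dose at which treatment starts. On that reading the problem disappears. But the parenthesis defines the target as 1 g/kg/day and no section re-centres it. If the ordered dose is what is meant, the text should say so. The protocol also promises written procedures manuals and forms with clear definitions, but nothing shows that these would change the threshold.

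A second reply is that other controls would catch the error: orders stating daily volume and hourly rate, the two-nurse check, monthly review of dispensing records, investigator review at least monthly, and weekly team rounds. This stands as a reason to grade the point minor. It does not repair the rule, because none of these controls sets a different dosing threshold for CCI reports.

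A reader might infer that every properly modified dose must be reported as a deviation. The documents do not support that. The stated purpose of the tolerance favours a narrower reading that leaves ordered changes out. Even on the literal reading, a dose such as 1.1 can stay inside the range.

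**Conclusion.** The concern holds as a minor error in the written rule. With the target taken as the parenthesis defines it, a patient ordered 0.75 or 1.5 g/kg/day who is wrongly given 1.0 is not flagged by this rule at any permitted infusion time, although the dose is wrong by 33%. That does not depend on whether ordered changes count as variations. The over-reporting side does: it is certain for 0.75 and 1.5 on the literal reading only.

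A reader might go further and infer that such errors would go unnoticed, or that the trial's results are affected. Neither follows. The order-based checks may well detect the error, and no effect on endpoints, significance level or power is claimed. The documents do not say how often doses are modified, so the number of affected patients cannot be estimated.

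**What to change.** In the Omegaven administration item of Quality Control Method, replace the fixed target with wording such as: *The tolerance is the dose currently ordered for that patient under the protocol (initially 1 g/kg/day), plus or minus 1.5 hours at the ordered hourly rate. The 0.15 g/kg/hour limit continues to apply. Dose changes made under Dose Modification or for adverse events, and documented with date, old dose, new dose and reason, are not deviations. An order above 1.5 g/kg/day is a deviation.*

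Do not add a hard ceiling of 1.5 g/kg/day on the delivered dose. It would leave patients ordered 1.5 with no upward tolerance, which the section is meant to provide.

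The cost is a short amendment and one dose-change record, with no added tests or patients. The downside is that the CCI would no longer see permitted changes through deviation reports, so list them for the DSMB's six-monthly review.

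The fix has two limits. It still misses a mistaken 1.0 against an order close to 1.0, such as 1.125 over 10 hours. It also cannot detect an order that was never updated after a decision to change the dose.
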